*\*Note:* [name], our community research associate, will provide the training and fidelity monitoring of our community partners. She has been involved in statewide coordination of evidence-based health promotion programs for older adults in Wisconsin for over 9 years. Part of her responsibilities have included training, overseeing, and fidelity monitoring for health promotion programs (e.g., the “Chronic Disease Self-Management” program). In addition, [name] (co-investigator) has expertise in developing tools for fidelity monitoring for the health promotion program “Stepping On.” These fidelity tools are used nationally to ensure high fidelity with dissemination of falls prevention programs. Treatment fidelity implementation in the proposed study is consistent with NIH Behavior Change Consortium Treatment Fidelity Workgroup recommendations involving study design, training of providers, delivery of treatment, receipt of treatment, and enactment of treatment skills.

**Wait-List Control Group:** Older adults assigned to the control group will be instructed to go about their daily routines during the first 12 weeks of the study. They will complete, in the same manner as the intervention group, assessments at baseline, 4, and 12 weeks. The control participants will receive the *Stand Up & Move More* intervention after 12 weeks.

**Measures:** Data collection sessions will be held the week prior to beginning the intervention (at the introductory meeting), at 4 weeks (following the delivery of the intervention), and at 12 weeks (follow-up) at readily accessible sites in each county (see Appendices for a summary table of outcomes assessment). Assessments will be completed by assessors trained by [name]. The assessors will be blinded to group assignment, and every effort will be made to ensure the assessors remain blinded throughout the duration of the study.

**Sedentary behavior** will be assessed both subjectively and objectively: **(a)** Participants will be interviewed by the investigators about their time spent sitting during the day in different activities (e.g., watching TV, reading) over the past week using a previously validated questionnaire for older adults; **(b)** Activity Monitors will be worn at each assessment for one week: The *activPAL*

is a small accelerometer with an inclinometer to measure horizontal/vertical position of the device, and thus posture. This device will be affixed directly to the midline of thigh of the participant with a temporary non-allergenic adhesive. We will be using this device for the purpose of measuring time spent in sedentary behavior (hours/day) and to quantify the number of times sedentary behavior is disrupted by standing up. This device has proven to have excellent validity for the detection of posture. Also, the *Actigraph GT1M* is another small accelerometer worn on the hip. This device records the frequency of accelerations during ambulatory activities and can quantify physical activity across the entire exertion spectrum (sedentary time, light intensity, moderate intensity, and vigorous intensity physical activity). We used both monitors in our previous preliminary research and participants found them acceptable to wear; (c) Clickers and Daily Logs: participants will be given a small click monitor and instructed to press a button on the monitor every time they stand up. The monitor will record the number of stands the participant completes on a daily basis. Participants will complete a short daily log before they go to bed each day as a way to self-monitor what they did during the day to reduce sedentary behavior (e.g., how many times they stood and what they did while standing). We used daily logs in our previous preliminary research with minimal burden to participants.

*The Short Physical Performance Battery (SPPB)*: is an objective measure of functional performance that has been shown to be reliable and is sensitive to change. The test consists of a balance test, a 4-meter walk for usual gait speed, and a timed measure of chair stands.

*The MOS 36-Item Short Form Health Survey (SF-36)*: The SF-36 is a widely used measure of quality of life and has been shown to be reliable and valid. The SF-36 consists of subscales such as general health, physical function, vitality, social functioning, mental health, etc.

*PROMIS Questionnaires*: Pain and cognition (exploratory measures) will be assessed with the Patient-Reported Outcomes Measurement Information System (i.e., PROMIS questionnaires for pain intensity, pain interference, and cognition).

*Demographic and Health History Questionnaire*: At baseline, participants will be asked to complete a questionnaire regarding health status and demographic information (date of birth, sex, race, ethnicity, education, and marital status), current physical activity, smoking status, and current alcohol intake.

*Mediators of Behavior Change*: As suggested by NIH reviewers, we have added selected mediators of behavior change. Participants will complete questionnaires assessing self-regulation strategies, self-efficacy, and outcome expectancies.

*Adherence to the Intervention and Outcome Assessments*: Adherence to the *Stand Up and Move More* intervention workshop will consist of participants attending at least 50% of the sessions. As for outcome assessments, adherence to wearing the accelerometers will be defined as wearing the monitors 4 out of 7 days.

*Analyses*: The primary sedentary behavior outcome variables include total sedentary time, time spent sitting in long bouts (i.e.,  $\geq 60$  minutes), and sit-to-stand transitions as measured by the activPAL. These outcomes will be examined adjusting for monitor wear time if wear time differs between groups. We will also be able to analyze changes in specific domains of sedentary behavior (e.g., watching TV, reading) from data obtained from the sedentary behavior questionnaire. A 2 (groups) x 3 trials (pre, post-1, and post-2) repeated measures ANOVA will be used to examine differences between groups in changes in sedentary behavior before and following the intervention and control conditions. Similarly, for the secondary variables of physical activity, functional performance, health-related quality of life, and mediators of behavior change, a series of 2 x 3 repeated measures ANOVA's will be performed. Significant main effects and interactions will be assessed with planned contrasts. Effect sizes will be calculated to examine the magnitude of differences between groups as well as the magnitude of change from pre to post-intervention according to methods described by Cohen. In addition,

correlational analyses will be performed to examine the relationship between sedentary behavior and the secondary outcomes. Significance will be set at  $p < 0.05$ . {Note: since sample size was estimated for our primary outcome variable of sedentary behavior, we recognize the potential limitation of our sample for secondary outcomes. However, if one or more of the secondary outcomes shows a trend in the direction of significance and/or shows a moderate to large effect size, the number of participants can be expanded in subsequent research to address a specific hypothesis}.

*Note:* Multiple imputation will be used to account for missing data (and attrition) under a missing-at-random assumption using MICE package in R. Longitudinal models for the outcomes at the two post-intervention visits will adjust the pre-intervention value as a covariate and explicitly model changes in the outcomes over time. Intervention workshop will be included in the included model as a random effect to account for correlations in outcomes between subjects in the same workshop.

Feasibility: The feasibility of implementing the program by our community partners will be assessed after the refresher session (at 8 wks) via semi-structured interviews. The Aging Unit Directors and Health Program Facilitators will be interviewed and asked about their satisfaction with the intervention, the ease and difficulty of implementing the program, and their likelihood of sustaining the intervention outside of a research study {*Note: Aging Units offer evidence-based health promotion programs to older adults in their counties which are funded by the Older Americans Act (OAA). When a new health promotion program is shown to be evidence-based (i.e., effective, translatable), Aging Units can use OAA funding to support and sustain implementation of the program*}. Interviews will be transcribed and coded, classified, and organized into main themes using thematic analyses. Feasibility of completing the program by older adults will be assessed after the refresher session (at 8 wks) on the basis of program adherence (i.e., attendance) and participant satisfaction (brief questionnaire).

Cost Estimate: The cost of delivering the intervention in each county will be calculated based on the following: a) cost of training the health facilitators, b) payment of health facilitators for leading the workshops, c) cost of program materials, d) cost of transporting participants to the workshop sites (to ensure that older adults without transportation will be able to participate), and e) other miscellaneous costs incurred during the workshops (e.g., room rental).

Potential Problems and Alternative Strategies: We have considered the challenge of recruiting 80 older adults into this study. Based on our preliminary research, we believe we will be able to recruit the sample size (i.e., 10-15 older adults per group in each county) needed for this project based on the following: 1) there was high interest from older adults in our preliminary research, 2) we have established good working relationships with our community collaborators who have had substantial input into the design of the current project, 3) there are good working relationships between county Aging Units and the older adults they serve in their counties, and 4) we will provide transport for older adults who require transportation to the site. Each county will provide two workshops (one for the intervention group and one for the wait-list control group) over a two year period. If we are not able to reach our recruitment target in year one (recruit 3/4 of sample,  $n=60$ ) we will offer additional workshops or expand the program to other counties in the state in year two.

Collaboration with Community Partners: The intervention we are proposing to translate statewide was designed with community collaborators to be able to be implemented by State Aging Units in community settings. Our initial community partners who were instrumental in the design of the intervention included the Greater Wisconsin Agency on Aging Resources (GWAAR) and the Rock County Council on Aging. GWAAR provides community-based aging

services to 70 counties and 11 tribes and considers interventions to increase physical activity a high priority area. For this reason, GWAAR funded our preliminary research which consisted of developing the intervention and conducting preliminary testing in two communities in Rock County, WI. The results indicated significant reductions in sedentary behavior, moderate improvements in physical activity, as well as large improvements in mobility and vitality. As a result of these findings, [name] from GWAAR, who as the Community Research Associate with the Community-Academic Aging Research Network (CAARN) works with research faculty and counties in Wisconsin put out a call to identify community partners who would be interested in participating in the proposed research. Thus, our community partners have expressed high interest in this project. In addition, there is high need in these counties. For example, Vilas County currently ranks 56 out of 72 while Rock County ranks 62 out of 72 in county health rankings. The directors of the Aging Units in these counties see the “Stand Up & Move More” intervention as a viable intervention for older adults in their counties with compromised health and physical limitations. While Iowa County ranks higher in the county health rankings (29 of 72), they have identified a lack of access to physical activity programs as a significant health risk factor. In addition, there are significant health disparities in Dane County. For example, African Americans in Dane County have higher rates of cancer, diabetes, disability, and physical inactivity than any other racial/ethnic group (HealthyDane.org). Therefore, we are including the older African American community from Madison, WI in the proposed project. An African American Program Manager will be hired to recruit and facilitate the project in the community. As recommended by African American community leaders, focus groups with older African American adults will first be conducted to ensure the intervention is culturally relevant and sensitive to the needs of the community. A facilitator from the UW Survey Center who is experienced in running focus groups will conduct 2 focus groups of 8-10 older African American adults. Results will be used to market and tailor the intervention to older African American adults. An African American facilitator will be hired and trained to deliver the intervention.

In sum, our community partners are very supportive of the proposed project and see high need for the *Stand Up & Move More* intervention, especially since the older adult population in these counties is projected to increase substantially in the future. For example, one in three individuals in Iowa County will be aged 60 years or older while 40-50% of the population in Vilas County will be over the age of 60 years by the year 2040. We believe we have an exceedingly strong partnership to be able to successfully conduct this important and promising research. The proposed project will provide an important step in developing effective strategies for maintaining independence in older adults through determining the feasibility and impact of a community-based intervention to break up sitting time.

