**Design:** As a next step, a randomized controlled trial will be conducted with a larger sample of older adults from underserved communities. Older adults from 4 counties in Wisconsin (i.e., Dane, Iowa, Rock & Vilas) will be randomized into intervention or wait-list control groups (Note: a block randomization scheme will be used blocking for age). Our pilot data suggests an intervention design of one session per week for 4 weeks with a refresher session at 8 weeks is feasible and likely to sustain behavior change. The primary outcome measure is sedentary behavior while the secondary outcome measures include physical activity, functional performance, and health-related quality of life. Assessments will be completed at baseline, after the intervention (4 weeks) and at follow-up (at 12 weeks as suggested by our community partners as being a reasonable time for the older adults in the control group to wait for the next workshop to begin). Feasibility of implementing the intervention will be assessed via semi-structured interviews of the health program facilitators, while feasibility of completing the *Stand Up & Move More* program by older adults will be assessed by program adherence and participant satisfaction.

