**Participants:** A power analysis was performed to estimate optimal sample size for detecting potential differences between intervention and wait-list control groups in sedentary behavior using a repeated measures design, with an alpha of 0.05, a power of 0.80, and a medium effect (0.57). Results from the G-power analysis indicated a total of 68 participants (34 per group) would be needed for the proposed study but we have increased sample size in anticipation of a potential attrition rate of approximately 20% (a minimum of 80 adults older than 55 yrs will be recruited). Four counties (Rock, Iowa, Vilas & Dane) will each recruit between 20–30 older adults who will be randomized to either the intervention group ( $n = 10–15$ ) or the control group ( $n = 10–15$ ). Inclusion criteria includes > 55 yrs, currently inactive or low active (i.e., < 60 min of physical activity/week), residents of Rock, Iowa, Vilas or Dane Counties, and residing in a home or an apartment. Exclusion criteria are low levels of sedentary behavior (i.e.,  $\leq 6$  hours/day); recent hospitalization (past month); uncontrolled medical conditions including uncontrolled hypertension (BP > 170 systolic or 100 diastolic), heart disease (symptoms of angina with minimal exertion in the past month), actively receiving chemotherapy or palliative care for cancer, stage 4 liver disease (e.g., cirrhosis with ascites or encephalopathy or history of

bleeding esophageal varices), end-stage renal disease (on dialysis or creatine > 4), or end-stage pulmonary disease (dyspnea at rest or with minimal exertion); severe arthritis or any orthopedic condition that could be made worse by standing up and moving more; inability to stand up without assistance of another person; and inability to speak or hear spoken English. Participants will be given a gift card up to \$50 upon study completion (\$20 for participating in the study plus \$10 per each of three assessments).

Recruitment of Participants: Staff from Aging Units in the four counties will recruit older adults from their counties for this study. Recruitment strategies include announcements in senior newsletters, at congregate dining sites, churches, and medical clinics. In addition, announcements will be posted on Aging Unit websites, and flyers will be sent to mailing lists of older adults in the various counties. These strategies were used in our pilot research and worked well in recruiting the estimated sample size.

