Older adults will be asked to break up prolonged sitting (1 hour or more) with short breaks, e.g., get up and move for a couple of minutes multiple times throughout the day. Following the format of our successful pilot, participants will be asked, initially, to break up sitting time an extra 3-5 times/day progressing to 10-12 times/day by week 4. During the sessions participants will strategize on ways they can break up their sitting time safely in their home environment. In subsequent sessions, participants will share strategies that worked for them as well as be introduced to a list of other strategies used by Gardiner et al. (e.g., standing up and getting a drink of water). This will provide participants with a wide range of strategies and participants will choose which strategies to adopt across the 4 weeks. Each session builds upon the previous one with new information provided during each session. An overview of the sessions follows (with a summary table located in the supplemental material):

**Session 1:** Introduction and overview; group discussion on time spent sitting during the day and then participants will be asked to reflect on their current sitting habits and record how many hours/day they typically spend sitting while watching TV, using the computer, socializing, eating, reading, and driving or riding in a car (awareness of current behavior); information will then be provided on sedentary behavior and the health consequences of sitting too much (information dissemination); discussion of how participants could stand up and move more safely in their home environment (recommended behavior: stand up and move an extra 3-5 times/day); modeling (group leader stands and encourages others to stand up and move); discussion of **goal setting** and participants set a specific manageable goal on how to stand an added 3-5 times/day for the next week; development of an action plan to meet the goal (*Note:* participants will be asked to rate on their action plans their confidence in meeting the goal on a scale from 1, not confident at all to 10, completely confident. If a participant rates their confidence  $\leq 5$ , the facilitator will revisit the action plan to help older adults develop a different strategy in order to feel more confident); and discussion of **self-monitoring** (i.e., use of a click monitor and completion of a daily log at the end of each day to be brought back to the next session).

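### Randomisation is by individual with no household rule, so an enrolled couple can be split between arms of an intervention practised at home; if that happens, the contrast shrinks towards zero

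*Combined protocol and SAP*

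**What the plan says.** All references are to the combined protocol and SAP, Research Design and Methods, unless stated.

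- **Unit of allocation.** Under Participants, the four counties "will each recruit between 20–30 older adults who will be randomized to either the intervention group" or the control group, with 10 to 15 per arm. Under Design, "a block randomization scheme will be used blocking for age". Age is the only blocking factor named. Block size and age bands are not given.
- **Who may enrol.** The criteria cover age, activity, sitting time, residence and health. None concerns a second member of the same household.
- **Recruitment.** The channels include newsletters, dining sites and churches, and "flyers will be sent to mailing lists of older adults in the various counties". The phone screen asks about the eligibility criteria only. The note to Table 2 places screening and randomisation before the introductory meeting, so no planned step identifies couples before allocation.
- **Where the behaviour happens.** Delivery is by small-group workshop at county sites, but "participants will strategize on ways they can break up their sitting time safely in their home environment", and click counters and daily logs are used at home. Under Previous Research, the strategies used most in the pilot were standing during television commercials and spreading out household chores.
- **Controls.** They are told to keep to their usual routine for 12 weeks. Contact between arms is neither restricted nor recorded.
- **Analysis.** The longitudinal model has a random effect for workshop and none for household.

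**The concern.** Community channels of this kind can reach both members of a couple, and nothing in the plan stops both from enrolling. Each would be allocated separately. A control who lives with an intervention participant may notice, and join in, the breaks taken at home. To the extent that this lowers the control's own sitting time, the estimated effect is too small at both follow-up visits. Because household is not recorded, the trial could neither correct for this afterwards nor show that it was negligible.

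The planned power leaves little room for such a loss. Preventing it takes one question on a call that is already planned.

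**Working it through.** **1. The plan's own figure.** The protocol's power analysis "indicated a total of 68 participants (34 per group) would be needed for the proposed study", from an effect of 0.57, alpha 0.05 and power 0.80. Read 0.57 as a standardised mean difference, so f = 0.57/2 = 0.285. Take the between-groups test with m = 3 measurements ("A 2 (groups) x 3 trials (pre, post-1, and post-2) repeated measures ANOVA") and an assumed correlation of 0.5 between visits, which the documents do not state:

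lambda = f² × N × m / (1 + (m − 1) × rho) = 0.0812 × 68 × 3 / 2 = 8.28

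This gives power 0.81 at N = 68 and reproduces the stated size. Eighty recruits less 20% leaves 80 × 0.80 = 64, where power is 0.785.

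**2. Chance that a couple is split.** For two people in the same balanced block of size b, the chance is (b/2)/(b − 1):

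- b = 2: 1.00
- b = 4: 2/3 = 0.667
- b = 6: 3/5 = 0.60

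For two people in different blocks it is about 0.50. Block size is not stated, and partners need not share a block or an age band. I use 0.50 to 0.667. The value for blocks of 2 is left out because nothing in the plan points to that size.

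**3. Dilution.** Assumptions, none of them from the documents: 4 to 12 couples among 80 people (10% to 30% of participants), and a share s = 0.5 of the effect passed to an exposed control. With 40 controls:

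- Low: 4 × 0.50 = 2 exposed; 2/40 × 0.5 = 2.5%
- High: 12 × 0.667 = 8 exposed; 8/40 × 0.5 = 10%
- No couples: 0%

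Power by the method of step 1, with the variance left unchanged:

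| Dilution | Effect | Power, N = 68 | Power, N = 64 | N for 80% |
|---|---|---|---|---|
| 0% | 0.570 | 0.81 | 0.785 | 68 |
| 2.5% | 0.556 | 0.79 | 0.76 | 70 |
| 10% | 0.513 | 0.72 | 0.70 | 82 |

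**4. What joint allocation costs.** Assume a spousal correlation of 0.3. Relative to independent participants, the variance of the arm difference is multiplied by 1 + 2 × 0.3 × (couples together − couples split)/80.

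- 12 couples: 8 split and 4 together gives 1 − 0.03 = 0.97. All together gives 1 + 0.09 = 1.09. The standard error rises by √(1.09/0.97) = 1.06, or 6%.
- 4 couples: 2 split and 2 together gives 1.00. All together gives 1.03. The standard error rises by √1.03 = 1.015, or about 2%.

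**5. Net effect on effect/SE.**

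- 12 couples: 0.90/√0.97 = 0.914 under individual allocation; 1/√1.09 = 0.958 under joint allocation.
- 4 couples: 0.975 against 1/√1.03 = 0.985.
- Break-even with 12 couples: 1 − 0.20s = √(0.97/1.09) = 0.943, so s = 0.28.

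If spill-over is below roughly 0.3, joint allocation costs a little precision. It removes the bias for any s.

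**The case against.** The best case against is that nothing shows the problem will arise. The documents report no couples in the pilot and expect none here. Both partners would have to meet every criterion, including low activity and more than 6 hours of sitting a day. Much of the intervention is personal (own goal, action plan, clicker and log), and the protocol itself argues that older adults need an intervention before they sit less. By week 4 a control has had at most four weeks of exposure while the recommended stands were still rising. A manual of procedures is mentioned under Data Management but is not among the documents, and it may hold a household rule. All of this stands. It limits the likely size of the bias; it does not put a safeguard into the plan as written.

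Four stronger readings are tempting, and the documents do not support them.

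- A reader might infer that age blocking makes splitting near certain. The raised probabilities hold only for partners in the same block, and the block size is unknown.
- A reader might turn the dilution into minutes per day using the pilot's 60 min/day. That is a change reported for the pilot's 4-week programme, for which no control group is described; it is not a between-arm contrast.
- A reader might infer that correlation between partners in opposite arms, left out of the model, is itself harmful. Positive correlation across arms reduces the variance of the difference (0.97 in step 4), so ignoring it is conservative.
- A reader might call the intervention home-based. Only the practice is at home; delivery is at county sites.

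**Conclusion.** The gap is real: followed as written, the plan can place two people who share a home in opposite arms, and it has no means of knowing that it did. The direction of the resulting bias is towards no effect. Its size cannot be computed from the documents. It is about 2.5% to 10% of the effect under the assumed couple rate, split rate and half spill-over, and zero if no couples enrol. The net gain in precision from joint allocation is small and can reverse when spill-over is weak, so the case for change rests on removing an avoidable bias at little cost. This is a cheap improvement to the design. It does not show that the stated sample size is wrong or that the comparison is invalid.

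**What to change.** - **Design:** state that eligible people who share a household receive one joint allocation, with the older member's age used for the block.
- **Phone screen:** ask whether another member of the household is taking part or intends to, and settle this before the household is randomised.
- **Data collection:** record a household ID.
- **Analyses:** add a household random effect, or household-clustered standard errors, to the longitudinal model beside the workshop effect. Without this, joint allocation would leave the within-arm correlation unmodelled.

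**Cost.** One screening question, one line in the randomisation procedure, one data field and one model term. The standard error rises by about 2% to 6% under a spousal correlation of 0.3. Arm sizes within a county may differ by one or two. A county that recruits exactly 20 has no slack against the range of 10 to 15 per workshop, since an 11/9 split falls below it; a county with 22 could absorb a 12/10 split. The randomisation procedure should say how the range is kept.

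### Randomisation is blocked for age, but age is in neither outcome model; if age still predicts outcome after baseline adjustment, a little precision is forgone

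*Combined protocol and SAP*

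**What the plan says.** All of this is in the combined protocol and SAP, Research Design and Methods.

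- **Allocation.** Design states that "a block randomization scheme will be used blocking for age". The age categories are not given, and no other blocking factor is named. Participants says that each of four counties recruits 20–30 "older adults who will be randomized to either the intervention group" or the control group, 10–15 in each.
- **Analysis.** Analyses specifies "A 2 (groups) x 3 trials (pre, post-1, and post-2) repeated measures ANOVA", with monitor wear time added only if it differs between groups. The Note that follows adds: "Longitudinal models for the outcomes at the two post-intervention visits will adjust the pre-intervention value as a covariate". It also calls for a workshop random effect and multiple imputation. Age and county appear in neither description.
- **Workshops.** Potential Problems and Alternative Strategies gives two workshops per county, one for each arm.
- **Sample size.** The power analysis "indicated a total of 68 participants (34 per group) would be needed".

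**The concern.** When allocation is balanced on a factor that predicts the outcome, the treatment difference varies less from one randomisation to the next than an analysis ignoring that factor assumes. The factor's variance stays in the residual although the design has already removed it from the comparison. The estimate remains unbiased, but its standard error is too large, its confidence interval too wide and its test conservative. Analysing by the factor used in allocation recovers that precision.

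Age is the one factor the plan says it balances on, and it is left out of both models. At stake is a small amount of precision in a trial of about 80 people.

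**Working it through.** **Inputs from the plan:** alpha 0.05, power 0.80, effect 0.57, 68 participants, three assessments, two arms, four counties, two workshops per county.

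**Assumptions:** 0.57 is Cohen's d, so f = 0.57/2 = 0.285; the correlation between assessments is 0.5; the test is two-sided; R² is the share of outcome variance that age explains *after* baseline adjustment. The documents give no R², so a range is shown.

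**Step 1: reproduce the plan's figure.** For the between-groups effect in a repeated measures ANOVA with m = 3:

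λ = f²·N·m / (1 + (m − 1)ρ) = 0.285² × 68 × 3 / 2 = 8.285, so √λ = 2.878.

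With F(1, 66) the power is 0.810, and at N = 66 it is 0.798. The stated 68 is reproduced, and it involves no covariates.

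**Step 2: effect of omitting age.** With balanced age blocks and an individual-level model (no workshop effect):

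- SE overstatement = 1/√(1 − R²)
- Actual type I error ≈ 2[1 − Φ(1.96/√(1 − R²))]
- Power without age ≈ Φ[(2.878 − 1.997)/√(1 − R²)], where 1.997 is the critical t on 66 df
- Power with age: noncentral t on 65 df, noncentrality 2.878/√(1 − R²)

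| Residual R² of age | SE too large by | Type I error | Power without age | Power with age | Forgone, points |
|---|---|---|---|---|---|
| 0 | 0% | 5.0% | 0.811 | 0.809 | none |
| 0.02 | 1.0% | 4.8% | 0.8135 | 0.8171 | 0.4 |
| 0.05 | 2.6% | 4.4% | 0.8172 | 0.8288 | 1.2 |
| 0.10 | 5.4% | 3.9% | 0.8237 | 0.8483 | 2.5 |

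The power without age is a normal approximation. At R² = 0 it gives 0.811 where the exact value is 0.810.

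**Step 3: would county terms help in the same way?** With 4 counties × 2 workshops there are eight workshops. The arm comparison has 8 − 2 = 6 between-workshop df. Three county terms leave 3, and the critical t rises from 2.45 to 3.18. A simulation used 8.5 people per workshop, the Step 1 effect, no extra workshop variance and between-workshop df, and treated the control groups as workshops:

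| County share of variance | Power without county | Power with county |
|---|---|---|
| 0 | 0.67 | 0.50 |
| 0.01 | 0.65 | 0.51 |
| 0.02 | 0.62 | 0.51 |
| 0.05 | 0.55 | 0.52 |
| 0.10 | 0.45 | 0.54 |

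At a share of 0.05 the standard error falls from 0.284 to 0.236 when county is added. The 95% interval half-width nevertheless grows, from 2.45 × 0.284 = 0.70 to 3.18 × 0.236 = 0.75. At 0.10 it shrinks, from 2.45 × 0.321 = 0.79 to 3.18 × 0.230 = 0.73.

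**The case against.** The strongest reply is that the effect may be negligible. The longitudinal model already adjusts for the baseline value, which probably takes up much of what age predicts. If nothing remains, nothing is lost. Any error is on the conservative side, so there is no false-positive risk. All of this stands. It makes the point conditional and small, but it does not put age in the model.

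A reader might go further in three ways that the documents do not support.

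- **That standard errors are overstated and power is lost as a matter of fact.** The plan gives no variance explained by age or county. Nor does power fall below plan for this reason: the 68 was computed without covariates, and every power without age in Step 2 is above 0.80. If 80 are recruited and 20% are lost, 64 remain and the same formula gives 0.785. That gap comes from the attrition allowance, not from leaving out age.
- **That county was a stratification factor and should be a fixed effect.** Allocation within county is implied by the per-county split, but only age is named. The workshop random effect carries county variation without removing it from the arm comparison, so the question is fair. Step 3 shows, however, that county terms lower power at a county share of 0.05 or below and raise it at 0.10. The documents do not show which applies.
- **That the Step 2 percentages describe the planned model.** They come from an individual-level model without the workshop effect, and serve as a guide to size only. The lower powers in Step 3 reflect testing on few between-workshop df, not the omission of age.

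**Conclusion.** The point holds for age and is minor. The plan blocks allocation on age and then leaves age out of both outcome analyses. For an assumed residual R² of 2% to 10%, the standard error is about 1% to 5% too large and about 0.4 to 2.5 points of power are forgone; at R² = 0 there is no gain. These figures rest on balanced age blocks, an individual-level model, 68 people analysed, and an R² that the documents do not give. For county, what is established is a gap in the description: the plan does not say whether allocation was stratified by county or how county is to be treated beside the workshop effect.

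**What to change.** In the longitudinal model in the Note under Analyses, for every outcome, add age as a fixed effect alongside the baseline value: either the age block used in randomisation or continuous age. Include the same variable in the imputation model. State the age categories used for blocking.

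Do not require county fixed effects. Instead, state whether allocation was stratified by county, and how county is handled together with the workshop random effect.

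The cost is a few sentences and about 1 df for continuous age or a two-level block (one fewer than the number of blocks otherwise). Age varies between individuals, so it does not draw on the scarce between-workshop df as county terms would. Date of birth is already collected on the baseline questionnaire. The note to Table 2 puts randomisation before the introductory meeting, so the age block used at allocation should be kept in the dataset. Settling this before outcome data are examined also avoids a post hoc choice of covariates.
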